6.9.2 Primary Objective analysis

The incidence of hemorrhage AEs and the incidence fracture AEs reported by investigator, including all AEs, ADRs, grade 3-5 AEs, grade 3-5 ADRs, SAEs, and SADR will be analyzed and reported as categorical variables.

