5 OBJECTIVES

5.1 Primary Objective

- 1) To monitor the risk of occurrence of hemorrhages and fractures during the administration of belzutifan in subjects with RCC. In doing so, we will observe the percentage of subjects occurring hemorrhage and fractures during the administration of belzutifan, and contrasted the results obtained in this study with the percentage of subjects occurring the AEs observed in the everolimus group of the Study 005.

To address the Primary Objective, the incidence of hemorrhage AEs and the incidence of fracture AEs, including all adverse events (AEs), adverse drug reactions (ADRs), grade 3-5 AEs, grade 3-5 ADRs, serious AEs (SAEs), and serious ADRs (SADR) will be described.

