6.5.4 Subject observation

The treatment period is defined as the period from the start date of belzutifan administration until the date of the last administration. The observation period is defined as 12 months (52 weeks) from the start date of the administration. Adverse events will be collected throughout the treatment period and for 30 days following discontinuation of belzutifan treatment. However, the total follow-up period will not exceed the observation period [1 year (52weeks) from the first belzutifan treatment date].

Rationale for the observation period

In the 005 study, the median time to the first occurrence of hemorrhage was 84 days (range: 2 to 728 days), and the median time to the first occurrence of fractures was 277.5 days (range: 5 to 639 days). Additionally, most of the adverse events considered for safety concerns in this survey occurred within three months of the start of administration. To confirm the occurrence status (incidence rate, severity, treatment details, etc.) of these events, a 12-month (52-week) observation period was set.

¹ Any number or symbol that allows the investigator to identify the patient (no patient information such as medical record number required)

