6.5.6 Entry into the case report form and transmission

The investigator will document the information collected during the treatment and observation period in the (e)CRF.

For the subjects for whom follow-up becomes difficult (e.g., transfer to other hospital, etc.), the information which can be collected until the last observation will be documented in the electronic (e)CRF.

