Adverse events will be collected throughout the treatment period and for 30 days following discontinuation of belzutifan treatment. The follow up period for each subject will vary according to the treatment of belzutifan, but the maximum follow-up period will not exceed the observation period [12 months (52weeks) from the first date of belzutifan treatment.]

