6.9 Data Analysis and Statistical Analysis

Each endpoint will be analyzed using descriptive statistical methods such as mean, standard deviation, median, interquartile range, and/or minimum/maximum/range for continuous variables. For any categorical variables, frequency and percentage will be reported.

Each evaluation item will be subjected to descriptive statistical analysis in accordance with the statistical analysis plan.

The safety and effectiveness in subjects who are in violation of this protocol including inclusion/exclusion criteria (i.e. protocol violation cases) will be separately presented.

Patient background (age, sex, pregnancy status, lactation status, medical history and comorbidities, prior treatments/concomitant medications, etc.) will be summarized descriptively.

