6.9.1 Subject composition

Subject attrition will be reported, including:

- Number of the registered subjects
- Number of the subjects for whom the study form has been collected
- Number of the subjects for whom the study form has been finalized (Number of subjects whom the survey form has been quality checked per 6.5.8)

- Number of the subjects included in safety tabulation/subjects excluded from the tabulation and the reason

The subjects that meet the criteria for safety analysis, are treated with belzutifan at least once, complete at least one follow up visit (e.g., re-visit etc.), and are identified by an investigator whether AE occurred or not will be included in the subjects for the safety evaluation. The ‘safety tabulation’ group will be used for all analyses below unless otherwise noted.

- Number of the subjects included in effectiveness evaluation/subjects excluded from the evaluation and the reason

Only subjects in which a) belzutifan was administered at the recommended dose throughout the observation period or until belzutifan discontinuation and b) have an effectiveness evaluation will be included in the effectiveness analyses.

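### The primary contrast sets a crude percentage of subjects against the Study 005 everolimus percentage, although time at risk varies by subject, is capped at 52 weeks in the survey, and need not match Study 005

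*Protocol*

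**What the plan says.** Section 5.1 makes the percentage of subjects with hemorrhage and with fracture during administration the primary measure, and states its use: "contrasted the results obtained in this study with the percentage of subjects occurring the AEs observed in the everolimus group of the Study 005". Section 6.9.2 lists the event classes, ending "SAEs, and SADR will be analyzed and reported as categorical variables". Section 6.9 explains what that means: "For any categorical variables, frequency and percentage will be reported".

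Time at risk is defined elsewhere and differs between subjects:

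- Section 6.5.4: "Adverse events will be collected throughout the treatment period and for 30 days following discontinuation of belzutifan treatment", with a ceiling of 52 weeks from first dose.
- Section 6.7.3: "The follow up period for each subject will vary according to the treatment of belzutifan".
- Section 6.5.6, on transfer and similar cases: "the information which can be collected until the last observation will be documented in the electronic (e)CRF".
- Section 6.9.1 admits to the safety set treated subjects who "complete at least one follow up visit (e.g., re-visit etc.), and are identified by an investigator whether AE occurred or not". No minimum time at risk is required.

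Section 6.9.4 makes the comparison with Study 005 qualitative and untested, and promises to report differences in methods and population. Section 6.10 asks for caution. Neither names time at risk.

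**The concern.** A percentage of subjects depends on both the event rate and how long subjects are watched. Used alone, it describes what happened to treated patients while they were followed. Set beside a percentage from another study, it can be read as a comparison of risk only if time at risk is similar, and nothing in the protocol secures that. A short treatment course in routine practice would lower the survey's percentage and look reassuring. A comparator treated for a shorter time would make belzutifan look worse.

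Hemorrhage and fracture are the important potential risks in the Japanese risk management plan (section 4), and section 3 says the survey's results feed a review of that plan. The reader of the report should be able to tell a difference in risk from a difference in observation time.

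**Working it through.** **The plan's own figures.** Section 6.3 gives 47/372 = 12.6% hemorrhage, 14/372 = 3.8% Grade 3 or higher, 18/372 = 4.8% fracture and 8/372 = 2.2% Grade 3 or higher. Its sample size reproduces: with X binomial (403, 0.038), P(X ≥ 11) = 0.9005, and 403 is the smallest N reaching 90%. (With the unrounded 14/372 the probability is 0.894 and N would be 407.) The sample size is not at issue.

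**Step 1: observation windows.** The survey stops at 52 weeks = 364 days. Section 6.5.4 reports Study 005 first hemorrhages from day 2 to day 728 and first fractures from day 5 to day 639. Some Study 005 first events therefore fall beyond the survey's window. The section does not say which treatment group these onset times describe.

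**Step 2: sensitivity to observation length, from the protocol's figures.** Assume the onset medians in 6.5.4 (84 and 277.5 days) belong to the 47 and 18 subjects in 6.3.

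- Hemorrhage: the 24th of 47 first events falls at the median, so about 24/372 = 6.5% had an event by day 84, against 12.6% overall.
- Fracture: half of 18 is 9, so 9/372 = 2.4% had an event by day 277.5, against 4.8% overall.

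This shows that the percentage depends on when observation ends. It does not forecast the survey's result, because the survey's cap is day 364 and not day 84 or day 277.5.

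**Step 3: sampling error for scale.** The 95% half-width at n = 403 is 1.96 × √(p(1−p)/403), which is 3.2 points at 12.6% and 2.1 points at 4.8%.

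**Step 4: illustration with assumed exposures.** The following are all assumptions: a constant hazard λ = 0.015 per month, exponential time on treatment with rate μ = ln 2 / median, a one-month window after stopping in both studies, and a cap C of 12 months in the survey and 30 months in Study 005. The expected percentage is

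1 − [ e^(−λ) · μ/(μ+λ) · (1 − e^(−(μ+λ)(C−1))) + e^(−μ(C−1)) · e^(−λC) ].

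| Assumed median months, survey / everolimus | Mean months at risk | Percentages at equal hazard | Ratio |
|---|---|---|---|
| 10 / 3 | 8.70 / 5.32 | 12.1% / 7.5% | 1.61 |
| 8 / 4 | 8.09 / 6.73 | 11.3% / 9.3% | 1.22 |
| 4 / 4 | 5.91 / 6.73 | 8.3% / 9.3% | 0.89 |
| 4 / 6 | 5.91 / 9.35 | 8.3% / 12.6% | 0.66 |
| 3 / 6 | 4.99 / 9.35 | 7.1% / 12.6% | 0.56 |

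The true hazard ratio is 1 in every row. The 4 / 6 row has a gap of 4.3 points, above the 3.2-point half-width. The 4 / 4 row has a gap of 1.0 point, well below it.

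Masking works the other way. A true hazard ratio of 1.5 appears as 12.2% against 12.6% (4 / 6 months), and a hazard ratio of 2 as 13.5% against 12.6% (3 / 6 months).

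The exposure-adjusted rate is 0.015 × 12 × 100 = 18 per 100 patient-years in both groups whenever the hazards are equal, whatever the treatment length.

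**Step 5: is the adjustment feasible?** Section 6.6 collects start, stop, adverse-event onset and last-observation dates, so time at risk can be computed for each survey subject. At Study 005 rates the survey expects 403 × 47/372 = 51 any-grade hemorrhages, 403 × 18/372 = 19.5 fractures and 403 × 8/372 = 8.7 Grade 3-5 fractures. About 9 events split over three time intervals is 3 per interval, too few for interval rates.

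**The case against.** The strongest reply is that the crude percentage answers the objective as stated. That objective is the share of patients with an event during administration in routine use, and stopping treatment is part of what is being described. This stands for the descriptive part, and it is why the percentage should stay. It does not carry over to the contrast with another study's percentage.

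The comparison is also qualitative and caveated, and the analysis plan, which is not shown, may add person-time tables. Both are fair. But the protocol itself names the percentage as the quantity to be contrasted. The caveats in 6.9.4 and 6.10 do not mention time at risk, and words alone cannot show how much of a gap is due to it.

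The allowance for dropout is small: 410 registered for 403 analysed, 7/410 = 1.7%. That allowance concerns entry to the safety set. A subject lost after one follow-up visit can remain in the denominator.

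Three stronger readings are tempting, and the document does not support them:

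- A reader might infer a large distortion by scaling the Study 005 percentages with a time-at-risk ratio of 0.5 to 2. At constant hazard, 1 − (1 − p)^r gives 6.5% to 23.7% for hemorrhage. No exposures are given, and section 6.5.4 says most safety-concern events came within three months, which fits a constant hazard poorly. If Study 005's 372-subject group is the reference, r = 2 also requires its mean time at risk to be at most 6 months, even if every survey subject completes 12. A median fracture onset of 277.5 days makes that doubtful.
- A reader might infer that early deaths are miscounted as event-free. A cumulative incidence with death as a competing event treats them the same way.
- A reader might infer that equal hazards could hide a difference. Only unequal hazards can be hidden.

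**Conclusion.** The point holds for the contrast and not for the percentage as a description. As written, sections 5.1 and 6.9.2 produce a comparison that mixes event risk with length of observation, under a 52-week cap that Study 005's onset times exceed. It can suggest a difference when hazards are equal or mask one when they differ.

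The direction and size cannot be stated, because the protocol gives neither treatment durations nor everolimus percentages. Under the assumptions in step 4 the ratio of percentages runs from 0.56 to 1.61 at a true hazard ratio of 1, and is close to 1 when treatment lengths are similar. Since the comparison is descriptive, the harm would be a misleading contextual reading and not a wrong test. The remedy is cheap enough to be worth making.

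**What to change.** 1. Keep the crude percentages in 6.9.2 as the on-treatment description.
2. Add to 6.9.2 first events per 100 patient-years at risk, for any-grade and Grade 3-5 hemorrhage and fracture. Time at risk ends at the earliest of first event, end of adverse-event collection (30 days after last dose, or 52 weeks), death, transfer or loss. Give rates by time interval for any-grade events only.
3. In 6.9.4, base the everolimus contrast on the same exposure-adjusted measure with the same 52-week cap, where the sponsor can tabulate it from Study 005. Otherwise show the exposure of both groups beside the percentages.
4. In 6.10, name differing time at risk as a limitation.

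The cost is two extra tables, a few sentences and, where possible, one tabulation from Study 005. No new survey data are needed. Two weaknesses should be stated with the rates: censoring at drug stop may be informative, and a rate averages over a hazard that may not be constant.

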6.9.3 Secondary Objective analysis

- 1) Patient demographic and clinical characteristics will be analyzed and reported as noted above according to whether they are a categorical or continuous variables for:

- a) the registered subjects
- b) the safety evaluation group
- c) by presence/absence of any adverse event
- d) by presence/absence of hemorrhage
- e) by presence/absence of fracture
- f) by presence/absence of anemia
- g) by presence/absence of hypoxia
- h) by presence/absence of intracranial lesions

- 2) The incidence of anemia AEs and the incidence hypoxia AEs, including all AEs, ADRs, grade 3-5 AEs, grade 3-5 ADRs, SAEs, and SADR will be separately analyzed and reported as categorical variables

- 3) The incidence of intracranial hemorrhage AEs with or without pre-existing intracranial lesions, including all AEs, ADRs, grade 3-5 AEs, grade 3-5 ADRs, SAEs, and SADR reported by the investigator will be separately analyzed and reported as categorical variables
- 4) The incidence of overall safety events reported by investigator, including all AEs, ADRs, grade 3-5 AEs, grade 3-5 ADRs, SAEs, SADR, unexpected SAEs, and unexpected SADR, will be analyzed and reported as categorical variables
- 5) The following will be analyzed and reported as categorical variables for a) hemorrhage AEs, b) fracture AEs, c) anemia AEs, d) hypoxia AEs, e) all AEs, f) all SAEs, g) all ADRs and h) all SADR reported by the investigator:
 - the proportion of subjects who interrupt drug due and the reasons for drug interruption
 - the proportion of subjects who discontinue drug and the reasons for drug discontinuation
 - the proportion of subjects with dose reduction and the reasons for dose reduction
- 6) The following will be analyzed and reported as categorical variables for the effectiveness analysis population based on the investigator's overall assessment after completion of administration, as detailed in the stand-alone statistical analysis plan:
 - ORR: best overall response rate (CR or PR)
 - DCR: best response rate of (CR, PR, SD)

6.9.4 Exploratory analysis

For all Primary objectives noted within, the results of this survey, as well as results from other relevant, published studies (LS005 etc.) will be qualitatively compared and reported. In addition to noting any similarities/differences in observed trends, any differences between this study and other relevant, published studies (LS005 etc.), including methodologies or study population, will be reported, as will any other limitations that may impede assessment of comparability. Given the inherent limitations associated with cross-study comparisons—such as differences in study design, patient demographics, and assessment methodologies—no formal statistical testing will be conducted. These analyses are intended to provide contextual understanding of the safety profile of belzutifan and are not designed to support formal statistical inference.

6.10 Limitations of the methodology

Due to its observational nature, there are several potential sources of bias including selection bias and information bias. In terms of potential selection bias, the study sites willing to participate in the study may not be fully representative of all sites treating patients of interest in Japan and may be different from patients treated in other healthcare systems in Japan or

other countries. As for information bias, there can be information loss during medical chart abstraction, based on recall, or transcription of information for database capture. As well, the adverse events are based on investigator reports and not defined by specific diagnostic tests. Additionally, causality assessment is decentralized and assessed by each investigator, therefore there may be differences in conclusions by investigator. Furthermore, as it relates to effectiveness data, response assessments may not be based on validated nor standardized measures (e.g., RECIST v.1.1). Lastly, the association of outcomes with treatment cannot be directly evaluated in this study given the lack of an internal comparator and inability to control for confounders or effect modifiers. There is also limited power and precision given the small sample size. As a result of the potential biases and limited power/precision, all analyses are descriptive in nature. Overall, these results offer a limited view of the safety/effectiveness of belzutifan and cannot be statistically compared to previous trials or other observational reports and should be interpreted with caution.

7 PROTECTION OF HUMAN SUBJECTS

Informed consent requirements will adhere to IRB/ERC requirements, applicable laws and regulations within Japan. Additional information on the informed consent process for this protocol are described in 6.5.2.

This study will require IRB/EC review at each site as noted in 6.5.1.

The Company recognizes that personal data may be received and understands that certain information may be considered sensitive in accordance with legal regulations. All information and personal data collected by the Company during the program will be preserved and protected according to local data privacy protection laws; if applicable, this data can be shared globally within the company with those handling adverse events, quality complaints or responding to medical queries, as well as with regulatory authorities.

8 MANAGEMENT OF ADVERSE EVENT AND REPORTABLE INFORMATION

Introduction

This is a hybrid data collection non-interventional study being conducted within routine medical practice. All direction for medication usage is at the discretion of a investigator in accordance with usual medical practice. No administration of any therapeutic or prophylactic agent is required in this protocol.

8.1 Adverse Event Reporting

Any Adverse Event (AE) including death due to any cause which occurs to the subject during the timeframe noted in the study protocol (during the administration period or within 30 days after discontinuation of belzutifan) after belzutifan is administered, must be reported to the Sponsor according to [Table 6](#) AE Reporting Timeframes and Process for Investigators / the Program Coordinator.

Please refer to Section 6.7.3 “Definition of safety related information” for the definition of each reportable information type and 6.7.4 “Evaluation of adverse event” for the detail.

Table 6 AE Reporting Timeframes and Process for Investigators / the Program Coordinator

Reportable information	Reporting timeframe Investigator to Sponsor/ Program coordinator to PV area	Reporting method
SAE/SADR	24 hours from receipt	If AE(s) occurs during the observation period, the investigator should promptly notify the MR, without waiting for the end of the observation period per the noted reporting timeframe by: 
 • Filling in the(e)CRF and submitting it • Contacting the MR in charge
NSAE/NSADR	10 calendar days from receipt	

8.2 AE Reconciliation

Reconciliation will be performed between the safety database and surveillance data to ensure all reportable AEs were reported and received. Starting from when the first patient is enrolled through the end of data collection, all AEs will be reconciled on a periodic basis.

9 PUBLICATION

[figure not shown]
The final results of the study may be published at academic conferences or in the article to be submitted. In both cases, the information on the subjects’ privacy and the sites will not be disclosed.

11 ORGANIZATIONAL STRUCTURE FOR CONDUCTING THE STUDY (JAPANESE)

< Organizational Structure for Post-Marketing Surveillance and Related Activities >

PART B PASS INFORMATION

Title	Special survey for belzutifan in patients with radically unresectable or metastatic renal cell carcinoma: a post-authorization safety study (PASS)
Protocol Version identifier	6482-045
Date of last version of protocol	09-DEC-2025
HMA-EMA Catalogues No:	Study not yet registered (anticipated 1Q2026)
Active substance	belzutifan (ATC code: L01XX74)
Medicinal product:	Welireg [®] , belzutifan
Joint PASS	No
Research question and objectives	
Among Japanese subjects with radically unresectable or metastatic RCC treated with belzutifan in routine practice,
 
Primary Objective
 
1) To monitor the risk of occurrence of hemorrhages and fractures during the administration of belzutifan in subjects with RCC. In doing so, we will observe the percentage of subjects occurring hemorrhage and fractures during the administration of belzutifan and contrasted the results obtained in this study with the percentage of subjects occurring the relevant AEs observed in the Everolimus group of the Study 005.
 
Secondary Objective
 
1) The overall safety of belzutifan, including safety concerns in subjects with RCC
 
2) The effectiveness of belzutifan in subjects with RCC

Country(-ies) of study	Japan

Author	
PPD [REDACTED] [REDACTED] Safety Program Operation MSD K.K. (hereafter referred to as Sponsor or MSD) [name]
 
PPD [REDACTED] [REDACTED] Merck Sharp & Dohme LLC, a subsidiary of Merck & Co., Inc., Rahway, NJ, USA

Marketing authorisation holder(s) including MAH Contact Person	
MSD K.K. (hereafter referred to as Sponsor or MSD) [name]
 
PPD [REDACTED] [REDACTED]

MSD Final Repository (REDS) Date	22-JAN-2026
Effective date:	15-JAN-2026
Health Authority Approval date:	23-JAN-2026

1. RESEARCH METHODS

1.1 Programming Quality

This study will incorporate the following quality checks for data analysis and reporting programming:

- Creating a program requirements and specification document (PRS)
- Developing and testing of statistical programs which includes ensuring the programs run successfully and all output are reviewed to ensure they meet the criteria included in the (PRS). This includes validating that all inputs (metadata or parameter values) are correctly specified in the programs and are consistent with the PRS.
- Independent Review and Testing, conducted by a second programmer to ensure that the input and outputs of the programs created by the first programmer meet the documented PRS. This includes the following 2 activities:
 - Review of code to ensure the program aligns with the PRS
 - Execution of code and review of results for some or all scenarios

And may include the following activity:

- Parallel programming of a small piece of critical code
- Independent Double Programming, conducted by second programmer. After programming is completed, the programs and results of the second programmer and compared to those of first programmer to ensure consistency. If discrepancies are found, the programmers will discuss and repeat steps until consistency is achieved.
- Review of outputs/results to ensure accuracy and format of each deliverable.

